5.5 STRATEGIES FOR RECRUITMENT AND RETENTION

The Sponsor (or designee) will identify clinical sites with:

- Access to subjects with neurodegenerative diseases (Parkinson's disease, MSA and ALS).
- Ability to perform ophthalmological procedures.

The clinical study is designed to recruit subjects through a network of physicians who routinely manage patients with neurodegenerative diseases and make referrals to study sites. The investigator will perform qualification assessments including confirmed diagnosis of neurodegenerative diseases.

6 STUDY DRUG

6.1 STUDY DRUG(S) ADMINISTRATION

6.1.1 Study Drug Description

AMDX-2011P, a retinal tracer (small molecule), is a phosphate prodrug hydrolyzed in vivo to the pharmacologically active molecule AMDX-2011.

	Active
Study Drug Name (INN)	AMDX-2011P
Type	Retinal tracer (small molecule)
Dose Formulation	Solution for injection
Unit Dose Strength(s)	mg
Dosage Level(s)	
 • Cohort 1 – 25 mg (1 mL) • Cohort 2 – 50 mg (2 mL) • Cohort 3 – tentative 100 mg (4 mL) • Cohort 4 – tentative 150 or 200 mg (6-8 mL) 
For Cohorts 3-4, doses to be confirmed by SMC based on emerging data from prior cohorts. Intermediate and/or higher dose levels may be explored.

Route of Administration	IV bolus injection over 2 minutes
Use	Experimental
Sourcing	The drug product is manufactured by Pace (Salem, NH), and provided centrally by the Sponsor or subsidiary, or designee.
Preparation	Individual doses of AMDX-2011P will be prepared by pharmacy staff and will be provided to study personnel for administration. Procedures relating to study drug preparation will be outlined in the Pharmacy Manual. AMDX-2011P will be provided frozen (at -20°C) in a 10 mL amber vial containing 5.5 mL of solution at a concentration of 25 mg/mL. It is a single dose vial. Vials must not be shared between subjects. The solution is light sensitive and must be protected from light at all times. AMDX-2011P must be thawed to room temperature prior to administration; once thawed, it must be used within 3 hours.
Post administration instructions	Subjects to be instructed to avoid direct sun and wearing light protective eye gear such as sunglasses for 24 hours after the dose. Subjects will be evaluated for signs and symptoms of phototoxicity.
Packaging and Labeling	The study drug will be dispensed in single administration vials. Study drug will be labeled as required per local regulations. All packaging and labeling operations for the study drug will be performed according to

	Active
	current Good Manufacturing Practices and the relevant regulatory requirements.
Storage Condition	Study drug is to be stored in a secure freezer (-20°C) and monitored (manual or automated) in accordance with the labeled storage conditions with access limited to the investigator and authorized site staff.

6.2 PREPARATION/HANDLING/STORAGE/ACCOUNTABILITY

6.2.1 Acquisition and Accountability

The investigator or designee must confirm appropriate temperature conditions have been maintained during transit for all study drug received and any discrepancies are reported and resolved before use of the study drug. Only subjects enrolled in the study may receive study drug, and only authorized site staff may administer study drug.

The investigator, or designee is responsible for study drug accountability, reconciliation, and record maintenance (i.e., receipt, reconciliation, and final disposition records). A record will be maintained by the investigational site staff member that will account for all dispensing and return of any used and unused study drug. Study drug administration will be at the clinical site. At the end of the study, the study drug will be reconciled, and a copy of the record given to the study monitor.

Clinical supplies, including study drug and inventory records, must be made available upon inspection by Sponsor or regulatory agency upon request. The study monitors will review the records along with other study records during monitoring visits.

Upon completion of the study, and after completion of study drug accountability by the study monitor, any surplus supplies will be destroyed upon receipt of written approval from the Sponsor (following the site's destruction Standard Operating Procedures) and evidence of destruction supplied to the study monitor.

Further guidance and information for the final disposition of unused study drugs are provided in the relevant manuals.

6.3 MEASURES TO MINIMIZE BIAS: RANDOMIZATION AND BLINDING

This study is open-label, assessor masked. All retinal images will be sent in batches to a central reading center for masked assessment. Assessors will be masked to type of subjects, their disease status, dose, and sequence of post-injection images. Investigators will not be masked to study drug. Please see Section 8.1.4 for further details on the central reading center procedures.

6.4 STUDY DRUG COMPLIANCE

Study drug will be administered at the study site by the investigator or designee, as per the SoA (Section 1.3).

A record of the dose of AMDX-2011P administered to each subject must be maintained and reconciled with study drug and compliance records. Study drug start time will also be recorded in the electronic case report form (eCRF).

6.5 TREATMENT OF OVERDOSE

For this study, any dose of AMDX-2011P greater than the assigned dose will be considered an overdose.

There is no specific treatment recommended to treat an overdose of study drug, and the subject should receive treatment directed towards any symptoms manifested.

In the event of an overdose, the investigator/treating physician should:

1. Contact the Study Medical Monitor immediately.
2. Closely monitor the subject for any AE/SAE and laboratory abnormalities until AMDX-2011P can no longer be detected systemically (at least 48 hours).
3. Document the quantity of the excess dose as well as the duration of the overdose in the eCRF.

6.6 CONCOMITANT THERAPY

Any medication or vaccine, including over-the-counter or prescription medicines, vitamins and/or herbal supplements, taken during the 7 days prior to the study drug administration will be recorded and reviewed by the investigator (or designee) to determine whether the subject is suitable for inclusion.

Treatment with another study drug, investigational device, or approved therapy for investigational use within 30 days (or five half-lives, whichever is longer) before anticipated dosing is prohibited.

The Study Medical Monitor (or designee) should be contacted if there are any questions regarding concomitant medications.

6.6.1 Prohibited Medications

Medications specifically prohibited in the exclusion criteria are not allowed during the ongoing study this include:

- Use of any new prescription therapies and vaccines within 7 days prior to study drug administration.
- Use of drugs with potential phototoxicity per Package Insert are prohibited within 48-hrs or 5-half-lives, whichever is longer, prior to first study drug until EOS visit, except for those required for treatment of underlying disease and/or AEs. Examples of such drugs include the following: Chloroquine (Aralen), hydroxychloroquine (Plaquenil), Thioridazine (Mellaril), Topiramate (Topamax), vemurafenib, voriconazole,

doxycycline, hydrochlorothiazide, amiodarone, furosemide, allopurinol, phenothiazine, and chlorpromazine.

The investigator is expected to discuss any questions regarding prohibited medications with the Study Medical Monitor (or designee) and/or referring physician if applicable. The final decision on any supportive therapy rests with the investigator.

6.6.2 Rescue Medicine

Not applicable.

7 STUDY DRUG DISCONTINUATION AND SUBJECT DISCONTINUATION/WITHDRAWAL

7.1 STOPPING RULES

The SMC will monitor safety throughout the study. The SMC will meet periodically to review available safety data to make decisions regarding continuation, modification, suspension, or termination of the study.

Study Stopping Rules

Dose escalation or administration of study drug in a dose cohort may be stopped and additional subjects will not receive study drug until a consultation has taken place among the investigator, the Study Medical Monitor (or designee), and SMC if one of the following circumstances occurs in subjects treated with AMDX-2011P unless it is determined by the SMC in consultation with investigator and the Study Medical Monitor that the occurrence is not related to the administration of the study drug:

- Two or more subjects in a cohort experience a Common Terminology Criteria for Adverse Events (CTCAE) Grade 3 or higher clinical or laboratory abnormality that is considered to be related to study drug by the investigator.
- An AE or group of AEs that singularly or in aggregate suggests to the investigator or Sponsor that the study drug is poorly tolerated and further treatment per protocol may not be safe.
- If one or more subject(s) in a cohort experience any treatment-related, treatment-emergent SAEs, dose escalation will be stopped to re-evaluate the dose in question.

If any of these criteria occur, the SMC will review all available data; if an event is determined to be related to a specific dose level, doses in subsequent cohorts may be modified or dose escalation may be terminated. Prior to any required dose level adjustment, the clinical and laboratory safety parameters from the previous dosing cohort(s) will be reviewed and discussed by the SMC to allow a recommendation on advancing to the next dose level. The suggested next doses may be the protocol-defined escalation dose, an equivalent dose, an intermediate dose, or an adjusted-downward dose based on evaluation of safety and tolerability data from previous cohorts.

The Sponsor, investigator, and the IRBs reserve the right to terminate or suspend the study at any time; the reason for such decision must be recorded. Should this occur, all data available will also be recorded in eCRFs. The investigator should notify the IRB in writing of the study's completion or early termination.

7.1.1 Pregnancy

A female subject or a female partner of a male subject who becomes pregnant will be followed as described in Section [10.3](#).

7.2 DISCONTINUATION OF STUDY DRUG

Not applicable; this is a single dose study.

7.3 SUBJECT WITHDRAWAL FROM THE STUDY

- A subject may withdraw from the study at any time at his/her own request or may be withdrawn at any time at the discretion of the investigator for safety, behavioral, or compliance reasons.
- At the time of withdrawing from the study, if possible, an early termination visit should be conducted, as shown in the SoA (Section 1.3). See SoA for data to be collected at the time of study discontinuation and follow-up and for any further evaluations that need to be completed.
- The subject will be permanently discontinued from the study drug and the study at that time.
- If the subject withdraws consent for disclosure of future information, the Sponsor may retain and continue to use any data collected before such a withdrawal of consent.
- If a subject withdraws from the study, he/she may request destruction of any samples taken and not tested, and the investigator must document this in the site study records.

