8.4.4 Time Period and Frequency for Event Assessment and Follow-Up

The occurrence of an AE or SAE may come to the attention of study personnel during study visits and interviews of a study subject presenting for medical care, or upon review by a study monitor.

All AEs including local and systemic reactions not meeting the criteria for SAEs will be captured on the appropriate eCRF. Information to be collected includes event description, time of onset, clinician's assessment of severity, relationship to study product (assessed only by those with the training and authority to make a diagnosis), and time of resolution/stabilization of the event. All AEs occurring while on study must be documented appropriately regardless of relationship. All AEs will be followed to adequate resolution.

Any medical condition that is present at the time that the subject is screened will be considered as baseline and will be reported in the Medical History eCRF page, not as an AE. However, if the study subject's condition deteriorates at any time during the study, it will be recorded as an AE.

Changes in the severity of an AE will be documented to allow an assessment of the duration of the event at each level of severity to be performed. AEs characterized as intermittent require documentation of onset and duration of each episode.

The investigator will record all events with start dates occurring any time after informed consent is obtained until 7 days after the study drug administration for non-serious AEs or 30 days after the study drug administration for SAEs. At each study visit, the investigator will inquire about the occurrence of AE/SAEs since the last visit. Events will be followed for outcome information until resolution or stabilization.

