8.4.5 Adverse Event Reporting

[Table 7](#) below summarizes the different reporting periods for AEs, SAEs, and pregnancy.

Table 7 Adverse Event Reporting Periods

Type of Event	Adverse Event	Serious Adverse Event / SUSAR	Pregnancy
Reporting period	From consent until 7 days after study drug administration or until AE is resolved or no further follow-up is required. (from consent to dosing, only collect AEs related to study procedures)	From consent until: 30 days after study drug administration or until SAE is resolved or no further follow-up is required	From dosing until 30 days after study drug administration
Reporting Timelines to the Sponsor	Entered into the clinical database on an ongoing basis	Within 24 hours of the investigator's knowledge	Within 24 hours of the investigator's knowledge
Reporting Method	AE eCRF	AE eCRF and SAE form	Pregnancy Form

Abbreviation: AE, adverse event (AE); eCRF, electronic case report form; SAE, serious adverse event ; SUSAR, serious unexpected suspected adverse reaction.

Events that begin before the start of study drug but after obtaining informed consent will be recorded on the AE section of the eCRF and will be identified in the analysis as non-TEAEs.

All SAEs will be recorded and reported to the Sponsor or designee immediately and under no circumstance should this exceed 24 hours from site awareness. The investigator will submit any updated SAE data to the Sponsor or designee within 24 hours of it becoming available.

Investigators are not obligated to actively seek AEs or SAEs after conclusion of a subject's study participation. However, if the investigator learns of any SAE, including a death, at any time after a subject has completed the study, and he/she considers the event to be related to the study drug or study participation, the investigator must promptly notify the Sponsor or designee.

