3.3 Schedule of Evaluations and Analysis Visit Windows

The schedule of visits and procedures are provided in the study protocol AMDX-2011P-101, Version 5.0, Amendment 5, Section 1.3 and AMDX-2011P-001, Version 1.0, Section 1.3. The study consists of a screening visit, treatment day, and 1 follow-up visit. For purposes of analysis, nominal time points will be used in data summarizations. The following target windows are expected for each visit:

Visit	Target Day of Visit	Visit Window (Days) for Analysis
Screening	-42 to -1	-42 to -1
Treatment (Day 1)	1	1
Follow-up (Day 8)	8	8-14

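### Protocol 7.3 ends study participation for a dosed subject who withdraws, although 8.4.4 runs AE and SAE recording from dosing; and SAP 3.3 has no window for an early-termination visit on Days 2–7

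*Protocol*

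**What the plan says.** - **Protocol 7.3.** Besides leaving at their own request, a subject "may be withdrawn at any time at the discretion of the investigator for safety, behavioral, or compliance reasons". The consequence is: "The subject will be permanently discontinued from the study drug and the study at that time". The same section asks for an ET visit where one can be arranged and refers to the schedule of activities for its content.
- **Protocol 7.2**, on stopping study drug: "Not applicable; this is a single dose study".
- **Protocol 8.4.4.** Events are recorded from consent "until 7 days after the study drug administration for non-serious AEs or 30 days after the study drug administration for SAEs". Sites ask about events at each study visit and follow known events to an outcome. Table 7 in 8.4.5 gives the same periods.
- **Protocol 8.4.5.** "Investigators are not obligated to actively seek AEs or SAEs after conclusion of a subject's study participation". After completion, the remaining duty is to pass on an SAE that the investigator happens to learn of and considers related.
- **Protocol 8.4.3.1.** Someone who leaves because of an AE is to be urged to have an end-of-study assessment and to stay under medical care until the event settles.
- **Protocol 1.3.** Day 8, end of study and ET share one column, with a +2 day window.
- **SAP 3.3.** The windows are Screening (Days -42 to -1), Day 1 and Follow-up (Days 8–14). It adds that "nominal time points will be used in data summarizations". ET is not mentioned.

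**The concern.** In a multiple-dose trial, withdrawal for safety at least ends exposure. Here the whole exposure is one injection, so withdrawing a dosed subject removes no drug and only ends observation. The primary endpoint is the incidence, nature and severity of AEs and SAEs in everyone dosed. The SAP keeps a withdrawn subject in the denominator (SAP 4.1 and 6) and imputes nothing (SAP 6.3). A new event that nobody asks about therefore counts as no event, and the error can only lower the observed incidence.

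The second problem lies in the analysis. Laboratory, ECG and vital-sign results are summarised at protocol time points, with change from baseline (SAP 6.7). For an ET visit between Day 1 and Day 8 the SAP gives the programmer no rule. The results either disappear from the by-visit tables or blend acute values into the Day 8 row.

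**Working it through.** **1. The follow-up window.** SAP 1.1 extends the analysis window from +2 to +6 days. 8 + 6 = 14 matches the Days 8–14 in SAP 3.3; the protocol's own window ends on Day 8 + 2 = Day 10.

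**2. Days with no analysis slot.** Post-dose days 1–14, less Day 1 and Days 8–14, leave Days 2, 3, 4, 5, 6 and 7. These 6 days have no window. An ET visit on one of them takes place 1 to 6 days after dosing, against 7 days for Day 8. By actual day it is left out of the by-visit summaries. By nominal label the only protocol column it can carry is the shared Day 8/EOS/ET one. With an ET row for Days 2–7, no day from 1 to 14 is unassigned.

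**3. Follow-up time at stake for a Day 2 withdrawal** (1 day after dosing, with the Day 8 visit taken on its target day).
- AE period: 7 − 1 = 6 days remain.
- SAE period: 30 − 1 = 29 days remain on paper.
- A completer's last scheduled contact is Day 8, which is 7 days after dosing. The last 30 − 7 = 23 SAE days therefore have no scheduled contact for anyone.
- Loss specific to withdrawal: 29 − 23 = 6 days for SAEs, and 6 days for AEs.

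The schedule has no general visit between Day 1 and Day 8 (the sentinel's 24-hour evaluation aside). In practice the loss is the Day 8 inquiry, and an ET visit partly replaces it.

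**4. What those 6 days could do to incidence.** If one such subject has a new event that goes unrecorded, observed incidence falls by 1/3 = 33 percentage points in a 3-subject cohort, or 1/12 = 8 points in a 12-subject cohort.

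The chance of seeing at least one event is 1 − (1 − p)^n. The documents give no event risk, so I assume p = 10% to 20%. I treat the withdrawn subject as wholly unobserved, which overstates the loss.

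| Cohort | p | All observed | One unobserved |
|---|---|---|---|
| 3 | 10% | 0.271 | 0.190 |
| 3 | 20% | 0.488 | 0.360 |
| 12 | 10% | 0.718 | 0.686 |
| 12 | 20% | 0.931 | 0.914 |

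**5. How often.** No withdrawal rate is stated. If the early-withdrawal rate were 2%, 5% or 10%, the chance of at least one among 36 subjects would be 0.52, 0.84 or 0.98.

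**6. Do the other safeguards close the gap?** The ET visit captures what has happened by then. The supervision text in 8.4.3.1 and the follow-up to outcome in 8.4.4 concern an event already known. None of them provides for finding an event that begins after the ET visit.

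**The case against.** No passage says that recording stops at withdrawal. The 7- and 30-day periods are counted from dosing, not from participation. Protocol 7.3 also says "See SoA for data to be collected at the time of study discontinuation and follow-up and for any further evaluations that need to be completed", which can be read as leaving room for later contact. This stands as far as it goes: the text is in conflict and does not state a rule for discarding data. But the schedule to which that sentence points contains nothing after the ET column, and no passage says which section governs a withdrawn subject.

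Several stronger readings are tempting, and the documents do not support them:

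- *A reader might infer that safety data are lost at once, and mainly in subjects with tolerability problems.* Protocol 7.3 asks for an ET visit, and 8.4.3.1 deals specifically with those who leave because of an AE. Safety is one ground beside own request, behaviour and compliance.
- *A reader might infer that 29 of 30 SAE days are lost.* Completers have no scheduled contact for 23 of those days either.
- *A reader might infer that collected AEs drop out of the primary analysis.* TEAEs are defined by onset date without visit windows, those leading to discontinuation are counted (SAP 6.7), and all eCRF data are listed (SAP 6). Time in study is also summarised (SAP 6.1), so shortened follow-up would be visible.
- *A reader might infer that escalation decisions rest on mislabelled tables.* The safety committee reviews all available safety data through its own summary (Protocol 4.1 and 10.1.5), and the interim analysis uses individual listings (SAP 7). Neither depends on the SAP 3.3 windows.
- *A reader might take it as settled that ET values will be shown as Day 8.* The eCRF visit labels cannot be seen, so omission is equally possible.

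**Conclusion.** The point holds, at minor severity, in two parts.

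First, 7.3 and 8.4.5 together conflict with 8.4.4 for dosed subjects who withdraw, and new-onset events after the ET visit can go unsought. The loss specific to withdrawal is up to 6 days of AE and SAE ascertainment for a Day 2 exit, if the Day 8 visit would have been held on its target day. The 33-point and 8-point shifts need an early withdrawal, a later new event and a failure to record it, all in the same subject. The documents give no rate for any of these, and with a single follow-up visit at Day 8 the overall effect is probably small.

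Second, SAP 3.3 has no rule for ET results from Days 2–7, so laboratory, ECG and vital-sign values may be omitted from by-visit summaries or tabulated as Day 8. Recorded AEs, and hence the primary analysis of collected events, are unaffected.

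**What to change.** **Protocol.** Reconcile 7.3, 8.4.4 and 8.4.5. State that, for dosed subjects who have not withdrawn consent to follow-up, AE and SAE collection continues through the periods already in 8.4.4, by visit or telephone, after other study procedures stop. State also that the release in 8.4.5 from seeking events does not apply to these subjects until those periods end. Merely deleting the reference to leaving the study from 7.3 would not be enough: that section is about study withdrawal, and it would then address only a drug already given in full.

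**SAP.** In 3.3, tabulate ET assessments made before Day 8 in their own ET row, not under Day 8. In 6.7.1, state that ET and unscheduled post-dose ECGs count toward the per-patient ECG categories. Those categories are not limited by visit now, so this only makes the intention explicit. The SAP has no matching laboratory categories, so none need changing.

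**Cost.** A few sentences in the protocol, one extra table row and occasional telephone calls. Sample size is unchanged.
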